5.11.2. Additional Analyses of the Primary Outcome

The primary MMRM analysis model will be repeated using the PP and Completer populations as a sensitivity analysis. If the conclusion differs from that of all randomized patients, the data and analyses will be further investigated.

A secondary analysis model for the efficacy estimand will be an ANCOVA for HbA1c change from baseline to the study primary endpoint, using the model with strata (pooled country, type of basal insulin, and age group) and treatment as fixed effects and baseline as a covariate. Missing endpoints will be imputed using the LOCF approach using postbaseline data only.

5.11.3. Sensitivity Analyses for Missing Data

A missing-not-at-random-based analysis will be performed for both the efficacy and ITT estimands to assess sensitivity of departures from the missing-at-random (MAR) assumption. The tipping-point approach that will be used is similar to a progressive stress test (Ratitch et al. 2013). The basic idea is to impute the missing values and add a value (delta) to the imputed values of the experimental treatment group and perform an analysis for the primary endpoint on the delta-adjusted data set to see whether the conclusion of the primary analysis is overturned. If not, a larger delta is chosen and the process repeated until the primary result is overturned. If the delta required to overturn the primary result is not a plausible departure from MAR, then the primary result is robust to plausible departures from MAR. The initial delta is set to 0.1 with an increment of 0.1. Imputation under the noninferiority null method (where delta equals the NIM=0.4) will be included as a special case of the progressive stress test.

For the ITT estimand, the imputation of missing data will be as described for the FDA primary analysis, and ANCOVA on the change from baseline to Week 26 in HbA1c will be used.

For the efficacy estimand, the copy reference approach will be used to impute missing data and the reference group will be the Humalog treatment group. Imputation will be for all longitudinal visits.

Sensitivity Analyses for Missing Data due to COVID-19 pandemic:

Missing data due to the pandemic represents an extraordinary circumstance, and missing data could be more prevalent in some geographic regions than in others. Lilly has been following a mitigation plan that aims to reduce the impact from the pandemic. Nevertheless, Lilly expects missing data at the primary endpoint visit, Visit 15 HbA1c, for COVID-19 related reasons:

- COVID-19 infection (adverse event) or death caused by infection,
- Discontinuation of treatment due to COVID-19 related reasons,
- Discontinuation of study due to COVID-19 related reasons, and
- Completed the 26 week treatment period, but missed primary endpoint due to COVID-19 related reasons.

Given those extenuating circumstances, the imputation rule as described when introducing ITT estimand may not be appropriate because the team assumes these subjects were to adhere to the study procedure if not interrupted by the pandemic. Thus a sensitivity analysis will be performed by applying an alternative imputation rule. In particular, for these subjects, all available Visit 15 HbA1c values will be utilized to impute their primary endpoints, within each treatment arm. The original imputation rule will be applied to other patients. The process after the imputation is the same as that for ITT estimand.

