## 10. Statistical Considerations

### 10.1. Sample Size Determination

Approximately 708 patients will be randomized in order that 600 patients complete the study through the primary endpoint at Week 26.

Patients will be randomized in a 2:2:1 ratio to double-blind LY900014 dosed 0 to 2 minutes before meals, double-blind Humalog dosed 0 to 2 minutes before meals, or open-label LY900014 dosed up to 20 minutes after the start of a meal. Stratification will be by country, HbA1c stratum ( $\leq 8.0\%$ ,  $> 8.0\%$ ), type of basal insulin (insulin glargine, insulin detemir, or insulin degludec), and age group (1 to  $< 12$  years, 12 to  $< 18$  years).

Assuming a NIM of 0.4%, no true difference between treatment groups and an SD of 1.1%, 240 completers for each double-blind treatment group will provide greater than 95% power to show noninferiority between LY900014 and Humalog using the upper limit of a 2-sided 95% CI (LY900014–Humalog). This sample size also has more than 80% power to show noninferiority between LY900014 and Humalog using a 0.3% NIM at 26 weeks.

With the assumption a difference no larger than 0.07% between treatment groups and a SD of 1.1%, 240 completers of double-blind Humalog dosed 0 to 2 minutes before meals and 120 completers of open-label LY900014 dosed up to 20 minutes after the start of a meal will provide approximately 76% power to show noninferiority between open-label LY900014+20 and double-blind Humalog using a NIM of 0.4%.

Assuming a 15% dropout rate during 26 weeks of treatment, approximately 708 patients (283 patients in each double-blind treatment group and 142 patients in the open-label treatment group) will need to be randomized.

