#### **10.3.3.1.1. Sensitivity Analyses for Missing Data**

A missing-not-at-random-based analysis will be performed for both the efficacy and ITT estimands to assess sensitivity to departures from the missing-at-random (MAR) assumption. The tipping point approach that will be used is similar to progressive stress test (Ratitch et al. 2013). The basic idea is to impute the missing values and add a value (delta) to the imputed values of the experimental group and perform an analysis for the primary endpoint on the delta-adjusted data set to see whether the conclusion of the primary analysis is overturned. If not, a larger delta is chosen and the process is repeated until the primary result is overturned. If the delta required to overturn the primary result is not a plausible departure from MAR, then the primary result is robust to plausible departures from MAR. Imputation under the noninferiority null method, in which delta equals the NIM, will be included as a special case of the progressive stress test.

For the ITT estimand, the imputation of missing data will be as described for the FDA primary analysis and ANCOVA on the change from baseline to Week 26 in HbA1c will be used.

For the efficacy estimand, the copy reference approach will be used to impute missing data and the reference group will be the Humalog treatment group. Imputation will be for all longitudinal visits.

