For non-FDA submissions, the primary efficacy comparison will be based on the contrast between LY900014 and Humalog at Week 26 (Visit 15) from the MMRM analysis of change from baseline in HbA1c including data collected from all randomized patients prior to permanent discontinuation of IP through Week 26 (efficacy estimand). In contrast to the population of ITT estimand, randomized patients with a baseline and at least one postbaseline result will be included in the analysis. The model for the analysis of the primary efficacy endpoint of change from baseline in HbA1c will include the fixed class effects of treatment, strata (pooled country, type of basal insulin, and age group), visit, and treatment-by-visit interaction, as well as the continuous, fixed covariates of baseline value. An unstructured covariance structure will be used to model the within-patient errors. Significance tests will be based on LS means and Type III tests. If this analysis fails to converge, the following covariance structures will be tested in order:

- Toeplitz with heterogeneity
- autoregressive with heterogeneity
- compound symmetry with heterogeneous variances
- Toeplitz
- autoregressive
- compound symmetry without heterogeneous variances

The first covariance structure that converges will be used. The Kenward-Roger approximation will be used to estimate denominator degrees of freedom.

For both primary analysis approaches, LY900014 will be declared noninferior to Humalog if the upper limit of the 2-sided 95% CI for the LS mean difference in the change from baseline in HbA1c for LY900014 minus Humalog is below +0.4%. In addition, the 95% CI for the treatment difference will be compared to an alternative NIM of +0.3%. Both estimands will be tested at the full significance level of 0.05.

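### The efficacy-estimand tipping delta is read as a departure from MAR but starts from copy reference to Humalog, so it is modestly too large when LY900014 is observed worse

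*SAP*

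**What the plan says.** For non-FDA submissions the primary comparison is an MMRM with treatment, visit and treatment-by-visit terms, using data up to permanent discontinuation of IP (SAP 5.11.1). SAP 5.3 justifies it by MAR.

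SAP 5.11.3 adds a tipping-point analysis for this estimand. A delta is added to the imputed values of the experimental arm only, starting at 0.1 and rising by 0.1 until the primary result is overturned. A delta of 0.4, the noninferiority margin, is included as a special case. The rule for reading the result begins "If the delta required to overturn the primary result is not a plausible departure from MAR", in which case the primary result is called robust. No numeric limit for plausibility is given.

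The imputation to which delta is added is set in the same section: "the copy reference approach will be used to impute missing data and the reference group will be the Humalog treatment group". Protocol 10.3.3.1.1 agrees: "the reference group will be the Humalog treatment group". Neither document plans a tipping-point analysis starting from MAR for this estimand, or re-expresses delta relative to MAR.

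**The concern.** For a Humalog patient, copying the Humalog arm is the same as MAR. For an LY900014 patient it is not: the imputed values follow the Humalog mean profile, adjusted only through that patient's own earlier values. Delta = 0 therefore does not reproduce the assumption of the primary analysis, although the decision rule measures delta from that assumption.

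In a noninferiority trial the direction matters. If LY900014 is worse, copy reference moves its missing patients toward the comparator before any stress is applied. The first part of delta only undoes that move, and the reported tipping delta looks more reassuring than it is. In relative terms the effect is largest when noninferiority passes narrowly, which is when a stress test is most needed.

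**Working it through.** **Inputs**
- Margin 0.4, SD 1.1, 240 completers per blinded arm, 15% dropout (Protocol 10.1).
- Two-sided 95% interval: "Both estimands will be tested at the full significance level of 0.05" (SAP 5.11.1).
- Missing fraction m = 0.15. This assumes every dropout lacks an on-IP Week 26 value.
- Carry-over c = 0.26 to 0.63. This is not in the documents. It comes from assumed visit correlations falling from 0.85 to 0.62, with dropout spread over the visit intervals.

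**The plan's own figures.** The documents state no tipping delta, but the power figures that fix the standard error reproduce (normal approximation).
- SE = 1.1 × √(2/240) = 0.1004.
- Margin 0.4: Φ(0.4/0.1004 − 1.96) = 97.8%, against "will provide greater than 95% power to show noninferiority between LY900014 and Humalog".
- Margin 0.3: Φ(0.3/0.1004 − 1.96) = 84.8%, against "more than 80% power to show noninferiority between LY900014 and Humalog using a 0.3% NIM at 26 weeks".
- The 95% half-width is 1.96 × 0.1004 = 0.197, so noninferiority passes only if the observed difference is below 0.4 − 0.197 ≈ 0.20.

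**Formula.** Let d be the observed difference, LY900014 minus Humalog. With the half-width treated as fixed (large-sample approximation), the estimate after adding delta is:
- MAR start: d + m × delta
- copy-reference start: d − m(1 − c)d + m × delta

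Setting estimate + 1.96 × SE = 0.4 gives:
- delta(MAR) = (0.4 − d − 1.96 × SE)/m
- delta(copy reference) = delta(MAR) + (1 − c)d

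The gap (1 − c)d does not contain m.

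**Numbers**, with SE = 0.10 and m = 0.15. At d = 0.18, delta(MAR) = (0.4 − 0.18 − 0.196)/0.15 = 0.16. The gap runs from 0.37 × 0.18 = 0.07 to 0.74 × 0.18 = 0.13, so the plan's delta is 0.23–0.29.

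| d | delta from MAR | delta as planned | gap | first 0.1 grid value that tips: MAR / as planned |
|---|---|---|---|---|
| −0.10 | 2.03 | 1.95–1.99 | −0.07 to −0.04 | 2.1 / 2.0 |
| 0 | 1.36 | 1.36 | 0 | 1.4 / 1.4 |
| 0.10 | 0.69 | 0.73–0.77 | 0.04–0.07 | 0.7 / 0.8 |
| 0.15 | 0.36 | 0.42–0.47 | 0.06–0.11 | 0.4 / 0.5 |
| 0.18 | 0.16 | 0.23–0.29 | 0.07–0.13 | 0.2 / 0.3 |
| 0.20 | 0.03 | 0.10–0.17 | 0.07–0.15 | 0.1 / 0.1–0.2 |

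**Bound.** With c = 0 the gap equals d. It therefore cannot exceed about 0.20, two grid steps, in a trial that has passed noninferiority.

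**Simulation check.** This was small and rough: 283 per arm, three post-baseline visits, assumed correlation 0.6, 15% missing at Week 26, 60 replicates, 20 imputations. Among trials passing noninferiority, the mean gap was as follows.
- True d = 0.1: +0.01 if the effect is constant over visits, +0.04 if it grows.
- True d = 0.2: +0.02 and +0.11 respectively.
- True d = 0: about −0.02, where the mean observed difference was itself slightly below zero.

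The direction agrees with the formula. The size depends on how the effect develops over visits.

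**The case against.** The strongest reply is that nothing formal turns on this number. SAP 5.11.3 sets no numeric plausibility limit, and a shift of around 0.1 crosses no prespecified line. At d = 0.18 or 0.20 the result looks fragile from either start. Under the planning assumption of no true difference, an observed difference between 0.15 and 0.20 has probability Φ(2.0) − Φ(1.5) ≈ 4%, and about half of trials would see LY900014 better. Copy reference to Humalog plus 0.4 is also a natural form of the noninferiority-null case, and the per-protocol, Completer and LOCF analyses are planned as well. All of this stands and limits the weight of the point. It does not make delta a departure from MAR, which is how the SAP says it will be read. The other analyses do not supply an MAR-based delta either.

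The size rests on assumed carry-over. The MMRM includes only patients with at least one post-baseline value on IP (SAP 5.11.1). If the stress test uses the same set, the missing fraction falls below 15% and c tends to rise. That stands too. A lower missing fraction leaves the absolute gap unchanged and reduces it relative to delta.

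Three stronger readings are tempting and are not supported:
- **That the noninferiority conclusion is biased or the planned start is systematically lenient.** The primary MMRM does not use this imputation, and the sign of the gap reverses when LY900014 is better.
- **That the ITT stress test has the same fault.** Its copy reference uses retrieved dropouts of the same arm, which can be read as MAR given arm and IP discontinuation. Only the return-to-baseline fallback clearly departs from MAR, and neither borrows from Humalog.
- **That the point requires a stress test for LY900014+20.** That would be a separate request for completeness and does not follow from this mismatch.

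**Conclusion.** The point holds for the efficacy estimand: the starting imputation and the rule for reading delta do not match. When LY900014 is observed worse by d, the reported tipping delta is too large by (1 − c) × d. In HbA1c points this is about 0.04–0.07 at d = 0.10 and 0.07–0.15 at d = 0.18–0.20, usually about one grid step.

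These figures assume SE 0.10, c between 0.26 and 0.63, and a half-width that does not change with delta. The tipping deltas themselves, but not the gap, also assume 15% missing. The consequence is confined to the robustness statement for a result in which LY900014 is numerically worse. The primary analysis, alpha and sample size are untouched.

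**What to change.** In SAP 5.11.3, for the efficacy estimand:
1. Impute missing HbA1c within each arm under MAR, using the terms of the primary MMRM.
2. Add delta to the imputed LY900014 values on the existing 0.1 grid, and judge plausibility on that delta. At delta = 0 the result should closely match the primary MMRM, which gives a check on the programming.
3. Keep copy reference to Humalog plus 0.4 as a separately labelled noninferiority-null scenario, outside the departure-from-MAR rule.

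The cost is some SAP wording, one extra imputation run, and a slightly less favourable tipping delta when LY900014 is worse. Protocol 10.3.3.1.1 carries the same copy-reference wording. Under SAP 5.1, a change that does not alter a principal feature of the protocol can be documented with its justification in the SAP or CSR, without an amendment.

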5.11.4. Analysis of Gated Objectives

Gatekeeping strategy will be used to control the overall type I error for testing the following gated objectives: noninferiority of LY900014+20 to Humalog in change from baseline to the study primary endpoint in HbA1c and superiority of LY900014 compared with Humalog in change from baseline to the study primary endpoint in HbA1c.

Following the successful claim of the primary objective, the noninferiority between LY900014+20 and Humalog in HbA1c change from baseline will be assessed using the same approach for the primary objective (ITT estimand for FDA submission and efficacy estimand for non-FDA submissions) with a NIM of 0.4%. Only when the noninferiority between LY900014+20 and Humalog is demonstrated, the superiority of LY900014 in controlling HbA1c compared to Humalog will be assessed. The superiority assessment will be based on the above statistical approaches for the primary objective (ITT estimand for FDA submission and efficacy estimand for non-FDA submissions). If the upper limit of the 2-sided 95% CI is below zero, LY900014 will be declared superior to Humalog.

5.11.5. Other Secondary Efficacy Analyses

The analyses described in Section 5.11.5 to Section 5.11.7 will include data collected from all randomized patients prior to permanent discontinuation of IP.

The longitudinal observations of actual and change from baseline in HbA1c up to Week 26 will be analyzed using the same MMRM model as for the analysis of the primary outcome.

At each visit (including both telephone and office visits), the basal daily dose and prandial insulin dose at different time points (morning meal, mid-day meal, evening meal and other) taken 3 days prior to the visit will be collected in eCRF. The average daily basal insulin dose per visit for each patient will be used in the analysis. Similarly, the average prandial insulin dose for each meal category (ie, morning meal, mid-day meal, evening meal, snack, and other) will be calculated, and average daily prandial insulin dose calculated as the sum of these average prandial insulin meal doses will be used for analysis. If either average daily basal or average daily prandial insulin dose is missing, the total daily insulin dose and the prandial/total insulin dose ratio will be set as missing for analysis. The analyses of insulin dose (ie, actual and change from baseline in total, basal, prandial insulin dose and prandial/total insulin dose ratio), will use an MMRM model similar to that for the primary outcome with an additional term of HbA1c stratum ($\leq 8.0\%$, $> 8.0\%$).

Treatment comparisons for the proportion of patients with HbA1c $< 7.0\%$ and $< 7.5\%$ will be analyzed using a longitudinal logistic regression with repeated measurements conducted by a generalized linear mixed model including independent variables of treatment, baseline HbA1c value, visit, baseline HbA1c-by-visit interaction, and treatment-by-visit interaction. An unstructured covariance structure will be used. As a sensitivity analysis, the proportion of patients with HbA1c $< 7.0\%$ and $< 7.5\%$ at Week 26 (Visit 15), imputed using LOCF, will be compared using a logistic regression model with terms for treatment and baseline HbA1c value.

Three 7-point SMBG profiles are expected to be collected during the 2 weeks prior to specified visits. For each time point, the average of the corresponding SMBG values from the SMBG profiles will be used for analysis. The analyses of the SMBG variables will use an MMRM model similar to that for the primary outcome with an additional term of HbA1c stratum ($\leq 8.0\%$, $>8.0\%$).

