## **7.2. Method of Treatment Assignment**

Patients who meet all criteria for enrollment will be randomized to double-blind treatment or open label treatment at Visit 4. Assignment to treatment groups will be determined by a computer-generated random sequence using an interactive web-response system (IWRS). Patients will be randomized to double-blind LY900014, double-blind Humalog, or open-label LY900014+20 in a 2:2:1 ratio. Stratification will be by country, HbA1c stratum ( $\leq 8.0\%$ ,  $> 8.0\%$ ) based on HbA1c measured at Visit 1, type of basal insulin at randomization (insulin glargine, detemir, or degludec), and age group (1 to  $< 12$ , 12 to  $< 18$  years).

The IWRS will be used to assign all IP (blinded and open-label) during the study. Site personnel will confirm that they have located the correct prefilled pens by entering a confirmation number found on the prefilled pen carton into the IWRS.

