#### **10.3.3.2. Secondary Analyses**

Following the successful claim of the primary objective, the assessment of noninferiority between LY900014+20 and Humalog and superiority between LY900014 and Humalog in

controlling HbA1c will use gatekeeping strategy. The noninferiority between LY900014+20 and Humalog will be evaluated first with the significant level of 0.05 (from the primary objective). Once the noninferiority is achieved, the superiority test between LY900014 and Humalog will be performed with the significant level of 0.05 (from the gated noninferiority objective). Both the assessments will be based on the analysis approaches used for the primary objective (ITT estimand for FDA submission and efficacy estimand for non-FDA submissions).

HbA1c and change from baseline in HbA1c at all timepoints will be analyzed by the same MMRM model used for the primary analysis for the efficacy estimand. The noninferiority in change from baseline in HbA1c for LY900014+20 to Humalog will be based on the same model.

Additional continuous secondary efficacy variables, as well as the change from baseline for these variables, will be analyzed either by the MMRM or ANCOVA models described in Section 10.3.1 for the efficacy estimand.

Treatment comparisons for the proportion of patients with HbA1c < 7.0% and < 7.5% will be analyzed using a longitudinal logistic regression with repeated measurements conducted by a generalized linear mixed model including independent variables of treatment, baseline HbA1c value, visit, baseline HbA1c by visit interaction, and treatment by visit interaction. An unstructured covariance structure will be used. As a sensitivity analysis, the proportion of patients with HbA1c < 7.0% and < 7.5% at Week 26 (Visit 15), imputed using LOCF, will be compared using a logistic regression model including treatment and baseline HbA1c value in the model.

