5.2. Adjustments for Covariates

Stratification factors of this study include country, HbA1c stratum ($\leq 8.0\%$, $>8.0\%$), type of basal insulin at randomization (insulin glargine, detemir or degludec), and age group (1 to <12, 12 to <18 years). Stratification factors will be entered into the interactive web-response system (IWRS) for randomization and also collected in the database by electronic case report form (eCRF) or central laboratory. The analysis models will use the stratification factors as collected in the database.

For the primary analysis of HbA1c, the stratification factor of HbA1c stratum will not be included. Instead, the continuous value of baseline HbA1c will be included in the analysis models.

Other efficacy analyses will include the stratification factors as noted in Sections 5.11 and 5.12.

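### The HbA1c-target responder models omit age group and basal insulin type: no rule is broken, but a little power is given up and the fix is nearly free

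*SAP*

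**What the plan says.** Randomization is stratified by four factors. SAP 5.2 begins its list "Stratification factors of this study include country, HbA1c stratum", and protocol 7.2 completes it with "type of basal insulin at randomization (insulin glargine, detemir, or degludec), and age group".

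Secondary objective 8 compares the proportions of patients reaching HbA1c below 7% and below 7.5% at Week 26. The main analysis in SAP 5.11.5 is a longitudinal logistic regression, fitted as a "generalized linear mixed model including independent variables of treatment, baseline HbA1c value, visit, baseline HbA1c-by-visit interaction, and treatment-by-visit interaction". The sensitivity analysis takes Week 26 with LOCF, and the proportions "will be compared using a logistic regression model with terms for treatment and baseline HbA1c value".

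Protocol 10.3.3.2 gives the same two models: "independent variables of treatment, baseline HbA1c value, visit, baseline HbA1c by visit interaction, and treatment by visit interaction" for the first and "logistic regression model including treatment and baseline HbA1c value in the model" for the second.

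On which strata enter which model, SAP 5.2 says "Other efficacy analyses will include the stratification factors as noted in Sections 5.11 and 5.12".

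**The concern.** The responder endpoints are the HbA1c measurements cut at two thresholds. The continuous analysis of those measurements adjusts for pooled country, basal insulin type and age group. The responder analysis adjusts for none of them, and no reason is given. The HbA1c stratum is not a gap, because continuous baseline HbA1c stands in for it.

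Age is the factor most likely to matter. Protocol 7.2.1.1 sets a goal below 7.0% but allows a higher one, mostly below 7.5%, for younger children who cannot describe symptoms of hypoglycemia. These are the two responder cut-offs, so age may predict reaching them even after adjustment for baseline HbA1c.

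In logistic regression, leaving out a prognostic factor moves the treatment odds ratio toward 1 even when the arms are balanced on that factor, and some power is lost. What is at stake is a little sensitivity on one secondary objective and its consistency with the HbA1c analysis it accompanies.

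**Working it through.** **Step 1: which models carry which strata.**

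| Analysis | Place | Age group | Basal insulin type | Pooled country |
|---|---|---|---|---|
| Primary HbA1c (ANCOVA and MMRM) | SAP 5.11.1 | yes | yes | yes |
| Insulin dose, 7-point SMBG (modelled on the primary) | SAP 5.11.5 | yes | yes | yes |
| HbA1c targets, longitudinal | SAP 5.11.5, protocol 10.3.3.2 | no | no | no |
| HbA1c targets, LOCF | same | no | no | no |
| Hypoglycemia incidence, logistic | SAP Table ITSB.5.4 | yes | no | no |
| CGM targets, logistic | SAP Appendix 2.6 | yes | no | no |
| PedsQL ANCOVA | SAP 5.11.6 | no | yes | yes |
| Primary CGM ANCOVA | SAP Appendix 2.4 | yes | yes | no |

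The listed terms are the same in both documents. The other logistic models shown carry age group, so a binary outcome does not explain its absence. None of them carries basal insulin type, so the case for that factor rests on the stratification and the HbA1c models alone.

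**Step 2: approximate attenuation from omitting one factor.** The plan states no responder rate, power or sample size for objective 8, so there is no figure to reproduce. For a balanced binary factor with log odds ratio β omitted from a single-visit logistic model, the treatment log odds ratio is multiplied by about 1/√(1 + 0.346·β²/4).

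- Assumed odds ratio 2: β = 0.693, β²/4 = 0.120, factor 1/√1.0416 = 0.980, a loss of about 2%.
- Assumed odds ratio 3: β = 1.099, β²/4 = 0.302, factor 1/√1.1044 = 0.952, a loss of about 5%.

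**Step 3: simulation of both factors.** The one design input is the 240 completers per double-blind arm in protocol 10.1. Everything else is assumed: one Week 26 visit, a true conditional treatment odds ratio of 2.0, adjustment for baseline HbA1c, arms balanced on both factors, an even age split, and basal insulin reduced to two levels split 40/60. There were 3,000 runs per scenario, each fitted without and with the two factors.

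| Assumed odds ratios (age / basal) | Responders | Treatment OR without | Treatment OR with | Power without | Power with |
|---|---|---|---|---|---|
| 1 / 1 | 24.3% | 2.026 | 2.034 | 78.2% | 78.3% |
| 1.5 / 1.25 | 28.5% | 2.001 | 2.022 | 80.1% | 80.5% |
| 2 / 1.5 | 31.7% | 1.974 | 2.022 | 82.0% | 82.7% |
| 3 / 2 | 36.9% | 1.918 | 2.027 | 82.9% | 85.0% |

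- Shift in the odds ratio, last three rows: 1 − 2.001/2.022 = 1.0%; 1 − 1.974/2.022 = 2.4%; 1 − 1.918/2.027 = 5.4%.
- Power lost: 0.4, 0.7 and 2.1 points. One simulated power has a standard error of √(0.8 × 0.2/3000) = 0.7 points. Both models were fitted to the same data sets, so the differences are better determined than that, but the two smaller ones are close to nil.
- The gain from adjusting does not come from a smaller standard error. In the last row it is 0.229 without and 0.239 with the factors; the adjusted estimate simply lies further from 1.
- The first row shows that adding two uninformative factors costs nothing visible.

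**Step 4: type I error.** With no treatment effect and the same three pairs of omitted-factor odds ratios, rejection at the two-sided 5% level was 4.7%, 4.9% and 4.7% without the factors and 4.7%, 5.5% and 5.0% with them. The simulation standard error is √(0.05 × 0.95/3000) = 0.4 points, so all are compatible with 5%.

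**The case against.** The strongest reply is that this is a covariate preference. Covariate sets vary across the plan, as the table in step 1 shows, and basal insulin type appears in none of the other logistic models listed there. The age argument is also indirect: the stratum is 1 to under 12 against 12 to under 18 years, many children under 12 can report symptoms, and the documents give no responder data by age. The size and direction of any age effect are therefore assumptions. All of this stands. It weakens the case for basal insulin type more than the case for age group.

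A second reply is that more fixed effects could hurt convergence. SAP 5.11.5 asks for an unstructured covariance in the binary longitudinal model and, unlike SAP 5.11.1 for the MMRM, gives no fallback. That is a real but small downside, and a fallback rule answers it.

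Three stronger readings are tempting, and the documents do not support them.

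- A reader might infer that the SAP breaks its own rule on strata. It does not: SAP 5.2 defers to the lists in later sections, and protocol and SAP agree.
- A reader might infer that the responder test is invalid. Type I error is unaffected, and the shift in the odds ratio reflects a differently conditioned quantity, not a failure of randomization.
- A reader might apply the 1% to 5% shift to the main longitudinal model. Both calculations describe a single visit. If the unstructured covariance is on patient random effects, these would absorb much of an omitted patient-level factor. If it is a residual structure, the odds ratio is population-averaged. The SAP does not say which.

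**Conclusion.** The point holds as a minor improvement. Both HbA1c-target models leave out age group and basal insulin type without explanation, although the trial is stratified by both and the primary HbA1c models include both. For the LOCF logistic model the cost is about 1% to 5% in the treatment odds ratio and about 0.4 to 2 points of power. This rests on assumed odds ratios of 1.5 to 3 for age group and 1.25 to 2 for basal insulin type, on the simulated responder shares, and on a true treatment odds ratio of 2. The cost for the longitudinal model was not estimated. Objective 8 carries no multiplicity control (SAP 5.5), and no primary or gated claim depends on it. Support is firmer for age group than for basal insulin type.

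**What to change.** In SAP 5.11.5, add age group as a fixed effect to both responder models, and type of basal insulin as well. State in advance that basal insulin type is dropped if the unstructured longitudinal model does not converge or if a basal insulin category is too sparse. Judge sparseness on data pooled across arms, before unblinding. Pooled country can stay out because of sparse cells; say so in one sentence.

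The cost is SAP wording and up to three parameters (one for age group, two for the three basal insulin types), plus a small convergence risk in the longitudinal model. Since this does not appear to change a principal feature of the protocol, protocol 10.3.1 and SAP 5.1 allow it to be recorded with its reason in the SAP or clinical study report, without a protocol amendment.
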